#### Main outcomes

The primary endpoint was good neurological outcomes of OHCA patients, which were classified as

cerebral performance category I or II at discharge. The secondary endpoints were the survival to discharge and prehospital ROSC. The tertiary outcomes were the provision of bystander CPR, regardless of dispatcher-provided CPR instructions, and bystander defibrillation.

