Third, according to the DA-CPR protocol, the dispatcher asked two key questions regarding altered mental status and abnormal breathing. When a suspected arrest occurred, to issue an alert about an OHCA event, the dispatchers pushed a button to send a short text message containing the location of the cardiac arrest and the location of nearest available PAD to registered all volunteers within one geographic town according to a time window. This time window address-matched volunteers to their workplace or home address during the intervals from 6 AM to 22PM. The protocol for the TM alert service was not applied to all OHCA, especially in cases which occurred during the time interval from 00:00-05:59 and 22:00-23:59, because the night was regarded as an ineffective time to alert volunteers due to being too late.

The dispatchers, EMS crew, registered CPR volunteers, and medical record reviewers who were employed to review the hospital outcomes by the Korea CDC were blinded to the study intervention.

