### Study design

This was a non-randomized, pre- and post-intervention trial. Since the intervention program started in May 2015, the period from January 2013 to December 2014 was defined as the pre-intervention period, and the period from January 2015 to December 2016 was defined as the post-intervention period. The TM cases were defined as the cases for which an TM alert was sent. Other cases were defined as standard care cases (non-TM cases).

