#### Data collection and variables

We collected data from the Korean OHCA Registry including the ambulance run sheet, dispatch record, cardiac arrest in-depth registry, and medical records for outcomes from the Korea Centers for Disease Control and Prevention. We developed the TM alert system registry by linking the TM cases that had a message sent to the registered volunteers. We checked the OHCA registry to confirm whether or not the case was a real arrest. Such cases were excluded if they were not a cardiac arrest or death was confirmed at the scene and no transfer to the emergency department (ED) occurred.

The main exposure of interest was the intervention phase (before- and after-intervention periods), and the secondary exposure was TM sent from the TM alert system. Demographic factors that were collected included the following: date of arrest, time of the call (00:01-05:59, 06:00-11:59, 12:00-17:59, and 18:00-23:59), age, gender, and comorbidities (diabetes, hypertension, heart disease, and stroke). Community and EMS factors that were collected included the following: witness information, location of the arrest, bystander CPR, laypersons' use of a PAD, primary electrocardiogram (ECG) at the scene, EMS response time interval (RTI, from the time of the call to the time of EMS arrival at the scene), scene time interval (STI, from the time of arrival at the scene to the time of departure from the scene), transport time interval (TTI, from the time of departure from the scene to the time of EMS arrival at the hospital), prehospital airway management by an EMS provider (endotracheal intubation, supraglottic airway device, or bag valve mask). Hospital factors included the emergency department (ED) level (regional level 1 ED, local level 2 ED, local level 3 ED) and post-resuscitation care, such as percutaneous coronary intervention (PCI), targeted temperature management (TTM), and extracorporeal membrane oxygenation (ECMO).

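### The TM versus non-TM odds ratio counts bystander CPR and defibrillation already under way at the call, which the alert cannot have caused

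*Combined protocol and SAP*

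**What the plan says.** All references are to the combined protocol and SAP.

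- **Outcome (Main outcomes):** "The tertiary outcomes were the provision of bystander CPR, regardless of dispatcher-provided CPR instructions, and bystander defibrillation". No start time is required and nothing ties the outcome to the alert.
- **Exposure (Study design):** "The TM cases were defined as the cases for which an TM alert was sent". Every other case is non-TM.
- **Sequence (Intervention program):** "the dispatcher asked two key questions regarding altered mental status and abnormal breathing"; when an arrest is suspected, "the dispatchers pushed a button to send a short text message containing the location of the cardiac arrest". The alert is thus a manual step some time after the call begins.
- **Variables (Data collection and variables):** the community and EMS list runs "witness information, location of the arrest, bystander CPR, laypersons' use of a PAD, primary electrocardiogram (ECG) at the scene", followed by the EMS intervals and airway management. The response interval is measured "from the time of the call to the time of EMS arrival at the scene". No interval is measured from the alert or from the start of CPR.
- **Sources (same section):** the dispatch record is named as a source, and "We developed the TM alert system registry by linking the TM cases that had a message sent to the registered volunteers". The timestamps in either are not described.
- **Analysis (Statistical analysis):** logistic regression of bystander CPR and of defibrillation on TM versus non-TM. Model 1 adjusts for age, gender and comorbidities. Model 2 adds season, weekend, time of arrest, witness status and location. The sensitivity analysis restricts the hour of the call to 6 AM to 10 PM.

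**The concern.** A patient whose bystander was already giving CPR when the call was made has the outcome before the exposure can occur. Such patients enter both groups of the TM comparison. In the TM group their CPR is credited to an alert that had not yet been sent.

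This matters because the TM versus non-TM OR is the only adjusted estimate the plan specifies for bystander CPR and defibrillation, and bringing these about is what the alert is for. There are two separate consequences. CPR in progress that is unrelated to alerting pulls the OR below the effect in patients whom a volunteer could still help. CPR in progress that is related to alerting can produce an OR away from 1 when the alert does nothing. A caller's report of CPR might make the arrest more obvious, or might make the alert seem less necessary, so the direction cannot be predicted. Neither the adjustment set nor the restriction on hour of call addresses the order of events.

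**Working it through.** The plan gives no event rate, expected OR or sample size for these outcomes, so there is no figure to reproduce. All rates below are assumptions chosen for illustration.

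**Inputs**
- q = share of cases with CPR in progress at the call: 0.1, 0.2 or 0.3.
- a1, a0 = probability that an alert is sent with and without CPR in progress: a1 from 0.4 to 0.7, a0 = 0.5.
- b0, b1 = CPR uptake among the rest without and with an alert: b0 = 0.4; b1 = 0.4 (no effect) or 0.5 (true OR = (0.5/0.5)/(0.4/0.6) = 1.50).

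**Formulas**
- P(CPR | TM) = [q·a1 + (1−q)·a0·b1] / [q·a1 + (1−q)·a0]
- P(CPR | non-TM) = [q(1−a1) + (1−q)(1−a0)·b0] / [q(1−a1) + (1−q)(1−a0)]

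**Step 1: alerting unrelated to CPR in progress (a1 = a0 = 0.5), true OR 1.50.** At q = 0.2:
- TM: (0.10 + 0.20)/0.50 = 60%.
- Non-TM: (0.10 + 0.16)/0.50 = 52%.
- OR = (0.60/0.40)/(0.52/0.48) = 1.38.

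At q = 0.1 the OR is (0.55/0.45)/(0.46/0.54) = 1.43. At q = 0.3 it is (0.65/0.35)/(0.58/0.42) = 1.34.

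**Step 2: no alert effect (b1 = b0 = 0.4), alerting related to CPR in progress.** With a0 = 0.5 the cells without CPR are equal in the two groups, so OR = [q·a1 + 0.2(1−q)] / [q(1−a1) + 0.2(1−q)].

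| q | a1 = 0.4 | a1 = 0.6 | a1 = 0.7 |
|---|---|---|---|
| 0.1 | 0.22/0.24 = 0.92 | 0.24/0.22 = 1.09 | 0.25/0.21 = 1.19 |
| 0.2 | 0.24/0.28 = 0.86 | 0.28/0.24 = 1.17 | 0.30/0.22 = 1.36 |
| 0.3 | 0.26/0.32 = 0.81 | 0.32/0.26 = 1.23 | 0.35/0.23 = 1.52 |

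**Step 3: many non-TM cases could never be alerted.** Enrolment covers 48 months (January 2013 to December 2016). The program ran for 20 of them (May 2015 onward), with alerts during 16 of 24 hours. If all enrolled cases are compared (the plan does not say) and calls are spread evenly (assumed), the alertable share is 20/48 × 16/24 = 0.28. Scaling a1 and a0 by this share gives null ORs at q = 0.2 of 0.91, 1.09 and 1.18 in place of 0.86, 1.17 and 1.36. The full range becomes 0.88 to 1.25.

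**Step 4: restriction to cases with no CPR in progress (q = 0).** The formulas reduce to b1 and b0. The OR is then 1.00 with no alert effect and 1.50 with the true effect, whatever a1 is. In this model, restriction removes both consequences.

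**The case against.** The strongest reply is that the plan chose any bystander CPR as its outcome on purpose. If alerting is unrelated to CPR in progress, an OR of 1.38 is the correct effect of alerting on that outcome (52% to 60%), and 1.50 answers a different question. This stands: dilution alone is not bias. Classing late alerts as TM likewise follows the plan's as-sent definition and is not a fault.

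Second, the documents tie the alert to a suspected arrest and a time window, not to CPR status. A reader might infer that the TM estimate is shown to be biased. It is not: the bias requires a link between CPR in progress and the button push, which the documents neither establish nor exclude. A manual, non-randomized step leaves the link possible.

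Third, a reader might infer that alert and CPR times were never collected. The documents support only that they are neither listed nor used; the dispatch record and the TM registry may hold them. Equally, nothing confirms that they do, so an easy remedy cannot be taken for granted.

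Fourth, step 3 shows that the larger figures apply only if the comparison is confined to cases that could have been alerted.

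Finally, the problem is probably smaller for defibrillation, because a device usually has to be fetched. That is a judgement; the documents give no figure. None of these replies supplies a way to separate CPR already under way from CPR that could have followed the alert.

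**Conclusion.** The point holds as a limitation of the TM versus non-TM estimate that is worth correcting. Cases that already have the outcome at the call enter that OR, and no listed variable, model or sensitivity analysis separates them. With equal frequency in the two groups, the OR is valid for any bystander CPR but understates the effect in patients not yet receiving CPR (1.50 shown as 1.34 to 1.43 for 10-30% in progress). With unequal frequency it is biased in an unknown direction, with a null OR of 0.81 to 1.52, or 0.88 to 1.25 if all enrolled cases are compared. Every rate behind these ranges is assumed; the results show what is possible, not what occurred.

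A reader might extend the point to the trial's main result. The documents do not support that. Bystander CPR and defibrillation are tertiary outcomes and the TM alert is the secondary exposure. The primary before/after comparison of neurological outcome does not depend on this contrast.

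**What to change.** 1. In Data collection and variables, add a field for CPR or PAD use in progress at the call, taken from the dispatch record where it is recorded.
2. In Statistical analysis, add a TM versus non-TM analysis of both outcomes limited to cases with neither in progress at the call, with the same covariates. Keep the existing any-bystander-CPR analysis beside it. The call is a reference point that both groups share; non-TM cases have no alert time.
3. Report cases whose timing cannot be classified as a separate category, by group.
4. State as a limitation that CPR begun between the call and the alert is still counted.
5. Do not remove late alerts from the TM group alone. Non-TM cases have no matching exclusion, so cases with short response intervals would leave only one side.
6. If the field cannot be obtained, describe the OR as an association with any bystander CPR, not as an effect of the alert.

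The cost is abstraction of one field from a source the plan already names, plus SAP wording. The downside is fewer cases in the added analysis and some with unclassifiable timing.

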### Statistical analysis

The demographics of the registered volunteers, registered PADs, and the number of TM alerts sent during the study period were compared for the study setting. A descriptive analysis was performed to determine the distribution of the categorical variables (counts and proportions) and continuous variables (medians and inter-quartile ranges). The chi-square test was performed for categorical variables, and the Wilcoxon rank-sum test was performed to compare continuous variables across the intervention periods.

Adjusted odds ratios (ORs) with 95% confidence intervals (CIs) for bystander CPR and defibrillation by TM versus non-TM were calculated using multivariable logistic regression analysis with adjustment for potential confounders. Adjustment for age, gender, and comorbidities were included as confounders in Model 1, and time factors (season, weekend, and time of the arrest) and characteristics of the arrest (witnessed, location of arrest) in addition to the confounders in Model 1 were added in Model 2.

Multivariable logistic regression analyses for outcomes (good CPC, survival to discharge, and PROSC) were used. Model 1 was adjusted for demographic factors (age, gender, and comorbidities); Model 2 was adjusted for the demographic factors from Model 1 as well as time factors related to the event (season, weekday, and daytime), Utstein factors (initial ECG, witness, and place), and EMS factors (RTI, STI, TTI, and prehospital airway); Model 3 was adjusted for the same confounders as Models 1 and 2 as well as factors related to advanced hospital care (PCI, TTM, and ECMO).

For the sensitivity analysis, a final multivariable logistic regression analysis was conducted for the subgroup population when the call occurred during the study time (TM sent time), from 6 AM to 10 PM. The confounders were same as the main analyses for each outcome. The main exposure was TM (cases who received TM alerts) versus non-TM (cases who did not receive TM alerts) for bystander CPR and defibrillation during the before- and after-intervention periods for outcomes (PROSC, survival to discharge, and good CPC).

All the statistical analyses were conducted using SAS software, version 9.4 (SAS Institute Inc., Cary, NC, USA). P values were based on a two-sided significance level of 0.05.

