## Intervention program

In May 2015, Seoul launched the TM alert system, called the dispatch-activated neighborhood access defibrillation and cardiopulmonary resuscitation program ("NAD-CPR" program) in 5 districts serving a population of 2.2 million (Gangdong-gu, Gangbuk-gu, Nowon-gu, Seocho-gu, and Jungnang-gu). The intervention consisted of three major components: registration of volunteers after CPR training, active installation and registration of a PAD, and dispatcher activation of registered volunteers for bystander CPR and defibrillation.

First, the CPR volunteer network was organized for those who agreed to register for the TM alert system after completing the CPR training courses provided in participating district health center. The CPR network was explained to the all trainee when CPR training was conducted and the trainees voluntarily registered themselves to the network after training. They were trained with a 1-hour CPR training course and received a certification card from the city mayor. The volunteers' telephone number, workplace address, and home address were collected and transferred to the dispatch center to integrate with the EMS call system. For quality control of the CPR trainee, the volunteer registration remained valid for 2 years, and after that it was automatically removed. If someone want to remain in the network after two years, they should be attend CPR renewal course and register again. The program started in

2013 as a pilot program and was implemented in 2014.

Second, the Seoul health authority expanded the installation of PADs. All PADs were registered in the National Emergency Medical Center by the EMS Act, and the PAD registry was developed and recorded for use. The active installation and registration of the PADs were guided by each district's health authorities at predesignated places by the EMS Act, such as public and commercial buildings, traffic stations, sports and cultural areas, and large-sized apartments. The city government provided half of the financial support for PADs, and the remainder were deployed by the private sector.

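### The adjusted odds ratio for bystander CPR and defibrillation mixes the alert's effect with dispatcher recognition and calendar time, and the plan adjusts for neither

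*Combined protocol and SAP*

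**What the plan says.** - **Contrast.** In Statistical analysis, "Adjusted odds ratios (ORs) with 95% confidence intervals (CIs) for bystander CPR and defibrillation by TM versus non-TM were calculated". Model 1 has age, gender and comorbidities. Model 2 adds season, weekend, time of arrest, witness status and location.
- **Groups.** Study design defines TM as a case for which an alert went out, and "Other cases were defined as standard care cases (non-TM cases". Study population enrols from January 2013 to December 2016. No restriction of the comparator to the period after launch is stated.
- **How an alert arises.** Under Intervention program, the dispatcher works through the DA-CPR questions, and "When a suspected arrest occurred, to issue an alert about an OHCA event, the dispatchers pushed a button to send a short text message". Launch was in May 2015, and alerts went out only between 06:00 and 22:00.
- **Outcome.** Main outcomes counts "provision of bystander CPR, regardless of dispatcher-provided CPR instructions".
- **Declared exposure.** Under Data collection and variables, "The main exposure of interest was the intervention phase (before- and after-intervention periods"; alert sent is secondary. For bystander CPR and defibrillation, the only comparison of periods in the plan is the unadjusted one: "The chi-square test was performed for categorical variables".
- **Changes over time.** Intervention program reports that "the Seoul health authority expanded the installation of PADs", and its paragraph on the volunteer network dates the start to "2013 as a pilot program and was implemented in 2014".

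**The concern.** Two features of the TM group are related to the outcome without any action by a volunteer.

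The first is recognition. An alert requires the dispatcher to suspect arrest, and that same step leads to dispatcher-assisted CPR. Because the outcome counts CPR given on dispatcher instruction, exposure and outcome share a cause. Arrests that the dispatcher did not suspect can only be non-TM.

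The second is calendar time. TM cases can occur only in the last 20 of 48 months, while the comparator includes the whole pre-period. Training and defibrillator installation developed over the same years. Season, weekend and hour repeat every year or day and cannot absorb a multi-year trend. Witness status and location are at most partial proxies for recognition.

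Bystander CPR and defibrillation are tertiary outcomes, but they are the steps the alert targets, so readers will take this odds ratio as evidence on whether the alert works. The plan also calls dispatchers and volunteers blinded, although dispatchers send the alert and volunteers receive it. Blinding therefore cannot be invoked to protect this comparison.

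**Working it through.** The plan gives no expected rate, sample size or odds ratio for these outcomes, so there is no figure to reproduce. The check asks what TM versus non-TM odds ratio to expect if the alert does nothing.

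**Inputs from the documents:** 48 months of enrolment; alerts in months 29-48 (20 months); alerts in 16 of 24 hours; alerts only for suspected arrests.

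**Assumptions:** arrests uniform over months and hours; no alerts before launch; a study area limited to the five programme districts; recognition r of 50-70%, constant over time; an alert sent for every recognised arrest in alert hours after launch; all CPR and defibrillation rates; any trend a constant yearly multiplier g of the odds, centred at January 2015.

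**Step 1: who the controls are.**
- Largest possible TM share: (16/24) × (20/48) = 0.278.
- Pre-period share of non-TM at r = 100%: 0.5/(1 − 0.278) = 69%. In alert hours: 0.5/(1 − 20/48) = 86%.
- At r = 50% and 70%, all hours: 0.5/(1 − 0.278r) = 58% and 62%. In alert hours: 0.5/(1 − (20/48)r) = 63% and 71%.

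**Step 2: recognition alone.** Take alert hours, no trend, and CPR in 70% of recognised and 45% of unrecognised arrests.
- r = 50%: TM is 0.5 × 20/48 = 0.208 of cases, with CPR rate 0.70. Non-TM is 0.292 recognised plus 0.500 unrecognised, with rate (0.292 × 0.70 + 0.500 × 0.45)/0.792 = 0.542. OR = (0.70/0.30)/(0.542/0.458) = 1.97.
- r = 70%: the non-TM rate is (0.408 × 0.70 + 0.300 × 0.45)/0.708 = 0.594, and OR = 1.59.
- All hours (the main analysis): 1.51-1.87. The hours restriction does not cure the problem.

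**Step 3: trend alone.** Measured from January 2015, the mean time of TM cases is 38/12 − 2 = 1.167 years. With TM share s in alert hours, the non-TM mean is −1.167s/(1 − s). For r = 50% (s = 0.208) the gap is 1.47 years, and for r = 70% (s = 0.292) it is 1.65 years. At g = 1.10 the ORs are 1.10^1.47 = 1.15 and 1.10^1.65 = 1.17.

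**Step 4: both together.** Month-by-month mixture, alert hours, zero alert effect, r = 50-70%:

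| CPR, recognised vs unrecognised | No trend | 10% per year |
|---|---|---|
| no gap | 1.00 | 1.15-1.17 |
| 60% vs 55% | 1.09-1.14 | 1.28-1.31 |
| 70% vs 45% | 1.59-1.97 | 1.85-2.26 |
| 50% vs 60% (reversed) | 0.78-0.84 | 0.89-0.99 |

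Defibrillation, no recognition gap, base rate 0.5-2%, r = 50-100%: 1.00 with no trend, 1.15-1.21 at 10% per year, 1.42-1.68 at 30% per year.

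**Step 5: would the remedies work?**
- *Restricting to post-launch alert hours only.* In this model the controls are then all unrecognised, and at 70% vs 45% the OR is (0.70/0.30)/(0.45/0.55) = 2.85. Fixing calendar time alone can make the recognition bias worse.
- *Phase contrast.* Compare all arrests in alert hours, May 2015-December 2016 with May 2013-December 2014. Without trend the OR is 1.00 at every recognition gap in the table. At 10% per year it is 1.10² = 1.21 with no gap and about 1.20-1.21 across the gaps. It removes selection on recognition but not trend.

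**The case against.** **Training and defibrillators are parts of the programme, not outside confounders.** This stands as a point of interpretation. Both are listed among the programme's three components, so a phase odds ratio estimates the whole bundle, against a baseline that was already partly exposed in 2013-2014. It does not rescue the TM odds ratio, which is set up as a contrast on the alert itself. The plan gives no dates for the defibrillator expansion and no trend in either outcome.

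**The phase model carries at least as much trend.** Also true: 1.21 against 1.15-1.17 at 10% per year with no recognition gap. The gain is on recognition: 1.00 against 1.59-1.97 at 70% vs 45%. A trend term and a stated limitation are therefore needed.

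**The sizes are assumed and fall on both sides of 1.** Correct. They show what can happen with no alert effect; they are not estimates for this trial. They are also unadjusted, and witness status and location may remove part of the bias.

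**Scope is inferred.** That non-TM covers all four years follows from the definitions and the enrolment window, but the sentence on the sensitivity analysis is ambiguous. If post-launch controls were intended, recognition bias would remain. If the study area were the whole city (2.2 of about 10 million people in the programme districts), the pre-period share of non-TM would be at most 0.5/(1 − 0.22 × 0.278) = 53%, still about half.

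**Weight.** The outcomes are tertiary and the exposure secondary. That limits the severity but does not justify reading the odds ratio as an alert effect.

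**Conclusion.** The concern holds. Both adjusted analyses of bystander CPR and defibrillation, the main one and the 6 AM-10 PM version, use the same contrast and the same covariates, and neither handles recognition or calendar time. That follows from the plan's definitions and needs no assumed rate.

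The size does rest on assumptions. With zero alert effect, expected bystander-CPR odds ratios in alert hours ran from 0.78 to 2.26 over the scenarios examined. Upward bias is the likelier direction for CPR, because recognition is the step that leads to CPR instructions, but the documents give no rates to confirm it. For defibrillation the direction is less certain and depends mainly on defibrillator expansion and trend. Confidence is high that the odds ratio is not an alert effect, and low on how far it is off.

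This should be fixed before these results are interpreted. It does not touch the phase contrast for the primary endpoint.

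**What to change.** 1. **Add adjusted phase models for both outcomes.** Include all arrests with calls from 06:00 to 21:59, whether or not an alert was sent. Compare May 2015-December 2016 with May 2013-December 2014, so that calendar months match. Use the stated Model 1 and Model 2 covariates plus district. District is not in the listed variables, so confirm that it can be derived.
2. **Show a version with a calendar-time trend term.** State that residual secular trend cannot be excluded, that the estimate is for the programme as a whole, and that the earlier period was already partly exposed.
3. **Relabel TM versus non-TM as an exploratory association.** State explicitly which months the non-TM group covers, and clarify the exposure sentence in the sensitivity analysis.
4. **If the dispatch record holds recognition,** restrict both TM and non-TM to recognised arrests, 06:00-21:59, from May 2015, and report how many controls remain. The plan names the record but lists no such variable.
5. **Do not describe dispatchers and volunteers as blinded** for these outcomes.

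The cost is SAP wording and re-runs, mostly on data already held; date of arrest and time of call are collected. The phase model uses 40 of 48 months and alert hours only, so intervals widen, and the trend term widens them further. The recognised-only contrast may leave few and selected controls.

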## Study setting

In Korea, the national fire department exclusively operates the EMS system, and EMS CPR protocol follows the 2010 and 2015 American Heart Association (AHA) guidelines. Ambulance crews can provide CPR at the scene and during transport, but they cannot stop CPR in the field unless the return of spontaneous circulation (ROSC) occurs and cannot declare death in the field because only a physician can declare death. Seoul is a large metropolitan city with a single-tiered intermediate level EMS. The population of Seoul is approximately 10 million in an area of 605 km^2. One dispatch center is responsible for the entire city, and a DA-CPR protocol was adopted in late 2010. Seoul is composed of 25 administrative and health districts. Each district consists of a number of neighborhoods ('town level'). There are an average of 17 neighborhoods in each district (total 429 neighborhoods). Average population of districts is approximately 400,000 in an average area of 24 km^2 and the average population of the neighborhoods is 20,000 in an average area of 1.5 km^2.

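### The TM versus non-TM models ignore place, so the TM odds ratio may be confounded by neighbourhood or district and its confidence interval may be too narrow

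*Combined protocol and SAP*

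**What the plan says.** Under Intervention program, the alerts ran "in 5 districts serving a population of 2.2 million". Volunteers were trained and recruited through participating district health centres, and PAD installation was guided by each district's health authorities. When an arrest is suspected, the dispatcher's text message goes to "registered all volunteers within one geographic town according to a time window". Alerts are not sent at night: "The protocol for the TM alert service was not applied to all OHCA", with 22:00 to 05:59 left out.

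Exposure is set arrest by arrest under Study design: "The TM cases were defined as the cases for which an TM alert was sent", and every other case is non-TM. In the same section, "the period from January 2013 to December 2014 was defined as the pre-intervention period".

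Under Statistical analysis, odds ratios "for bystander CPR and defibrillation by TM versus non-TM were calculated using multivariable logistic regression analysis". Model 1 has age, gender and comorbidities; Model 2 adds season, weekend, time of arrest, witness status and location of arrest. For the clinical outcomes the plan says "Multivariable logistic regression analyses for outcomes (good CPC, survival to discharge, and PROSC) were used", with EMS and hospital covariates added in steps. The sensitivity analysis restricts the hours and keeps the same confounders. No model lists district or neighbourhood, and no random effect, GEE, robust variance or stratification is named.

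TM is the secondary exposure (Data collection and variables). Bystander CPR and defibrillation are tertiary outcomes (Main outcomes).

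**The concern.** Whether an arrest can draw an effective alert depends on where it happens, because volunteer recruitment and PAD placement are local. The chance that a bystander starts CPR anyway can also differ by place. Intervention program supplies a link between the two: volunteers register after CPR training, and that part of the programme was piloted in 2013 and implemented in 2014, before alerts began in May 2015. A neighbourhood with many trained residents could have both more alerts and more bystander CPR that owes nothing to the alert. A model without a place term cannot separate that from an alert effect.

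The second issue is precision. If arrests in one neighbourhood resemble each other in both outcome and TM status, a logistic model that treats them as independent reports too small a standard error.

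At stake is the only planned model that links alerts to bystander action.

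**Working it through.** The plan states no sample size, power or ICC, so there is no design figure to reproduce. The question is how large each effect could be.

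**Inputs from the documents.** Five districts at an average of 17 neighbourhoods give 5 × 17 = 85. The route by population gives more: 2,200,000 / 20,000 = 110. Alpha is 0.05, two-sided.

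**Assumptions, not in the documents.** About 3,000 arrests, all from the five programme districts; half in the post-period; 75% in alert hours; half of eligible arrests alerted; 50% baseline bystander CPR; outcome ICC 0.02-0.07.

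**1. Standard error by formula.** For an exposure that varies within clusters of mean size m, the ratio of true to reported standard error is

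sqrt(1 + (m − 1) × ICC of outcome × ICC of TM).

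With m = 3,000 / 85 = 35.3:

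| Outcome ICC | ICC of TM | Calculation | Ratio |
|---|---|---|---|
| any | 0 | sqrt(1) | 1.00 |
| 0.02 | 0.1 | sqrt(1 + 34.3 × 0.002) | 1.03 |
| 0.02 | 0.3 | sqrt(1 + 34.3 × 0.006) | 1.10 |
| 0.05 | 0.1 | sqrt(1 + 34.3 × 0.005) | 1.08 |
| 0.05 | 0.3 | sqrt(1 + 34.3 × 0.015) | 1.23 |

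An ICC of TM of 0.3 is already extreme if all four years are compared. A neighbourhood's TM share is 0.5 × 0.75 × p = 0.375p, where p is its alert probability. Even if p were 0 in half the neighbourhoods and 1 in the other half, the mean share would be 0.1875, the between-neighbourhood variance 0.1875² = 0.035, the total variance 0.1875 × 0.8125 = 0.152, and the ICC of TM 0.035 / 0.152 = 0.23. At outcome ICC 0.05 that gives sqrt(1 + 34.3 × 0.05 × 0.23) = 1.18. A true-to-reported ratio of 1.05, 1.10 or 1.20 turns a 5% test into a 6.2%, 7.5% or 10.2% test.

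At district level m is much larger. With 2,000 arrests (m = 400) and outcome ICC 0.01, the ratio is sqrt(1 + 399 × 0.01 × 0.1) = 1.18 at an ICC of TM of 0.1.

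**2. Simulation with true odds ratio 1.** Plain logistic regression of outcome on TM, without the planned covariates; 3,000 arrests, 85 neighbourhoods, 1,000 runs per scenario. The ICC is on the logit scale: between-place SD 0.25 gives 0.0625 / (0.0625 + 3.29) = 0.019, and SD 0.5 gives 0.25 / 3.54 = 0.071.

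| Alert probability across neighbourhoods | Mean odds ratio | SE ratio | 95% CI coverage |
|---|---|---|---|
| Constant | 1.00 | 0.99 | 95-96% |
| Varies, unrelated to baseline response | 1.00 | 1.00-1.03 | 94-95% |
| Varies, correlation 0.5, ICC 0.02 | 1.04-1.09 | 1.00-1.07 | 94% to 83% |
| Varies, correlation 0.5, ICC 0.07 | 1.10-1.17 | 1.05-1.06 | 84% to 62% |

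With 5 districts as the clusters, the SE ratio was 0.97-0.98 when alert probability was constant and 1.05-1.08 when it varied.

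**3. Other assumptions.** Two further simulations with correlation 0.3-0.5 and wide variation in alert probability gave null odds ratios of 1.05-1.08 (ICC 0.02) and 1.09-1.14 (ICC 0.05) in one, and 1.10-1.19 (ICC 0.05) in the other. Their SE ratios without correlation were 0.98-1.09 in the first. In the second, where neighbourhood effects were allowed to drift between periods, they were about 1.0-1.1 at ICC 0.02 and 1.14-1.20 at ICC 0.05. Restricting to alert hours did not help (1.06-1.15); comparing only post-period alert-hour arrests made the bias larger (1.08-1.23). Stratifying by neighbourhood, or adding a neighbourhood term, brought the estimate back to 0.99-1.02.

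**4. Sign.** At 50% baseline the simulated model is symmetric, so a negative correlation gives the reciprocals: 1 / 1.04 = 0.96 to 1 / 1.19 = 0.84.

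**The case against.** The strongest reply is that TM is not a neighbourhood-level exposure. It is set for each arrest, and non-TM cases arise in the same neighbourhoods at night and, if they are included, in 2013-2014. Much of the contrast is therefore within neighbourhood, and the plain standard error can be close to right. This stands. A reader might infer from alerts going out by town that the TM intervals are certainly too narrow. The documents do not support that: with no clustering of TM the ratio is 1.00 or slightly below.

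A reader might also infer that the TM odds ratio is inflated. That requires alert frequency to be positively related to baseline bystander response. Intervention program makes such a link plausible but does not show it, and its sign is unknown.

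Model 2 does list location of arrest, and the outcome models list place. Neither is defined. Place appears with initial ECG and witness status among the Utstein factors, so it most likely means type of place. If it meant district or neighbourhood, much of the confounding concern would fall away.

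Finally, the reach is limited to a secondary exposure and tertiary outcomes. That also stands. It lowers the priority without removing the gap.

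**Conclusion.** The omission is real: delivery is organised by district and town, and no listed model accounts for either. Its consequences are conditional. Confounding by place is the larger risk at neighbourhood level: under the assumed values, a null TM odds ratio moves to about 1.04-1.19, or to about 0.84-0.96 if the correlation is negative. Loss of precision is the smaller risk there, with an SE ratio of about 1.0-1.2 without correlation; it could be larger if the clustering is by district. These figures rest on about 85 neighbourhoods, about 3,000 arrests, outcome ICC 0.02-0.07 and correlation 0.3-0.5. Apart from the neighbourhood count, which follows from the setting figures, none of these values comes from the documents.

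Nothing here shows that the primary analysis is invalid. Period varies within every neighbourhood, so stable differences between places largely cancel from that contrast. The effect there should be smaller and was not sized. This is an inexpensive improvement worth making, not a fatal flaw.

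**What to change.** In the TM models, add district fixed effects and either a neighbourhood random intercept (PROC GLIMMIX) or neighbourhood-clustered standard errors (PROC GENMOD with REPEATED). For bystander CPR, also report a within-neighbourhood TM estimate, for example from logistic regression stratified on neighbourhood, beside the planned one. It should not simply replace the planned estimate, because it leans more on day/night and any before/after differences.

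For the period models and the outcomes likely to be sparse (good CPC, bystander defibrillation), use district terms with neighbourhood-clustered errors. Neighbourhood fixed effects risk strata without events and separation. Do not cluster on district: five clusters are too few for a robust variance. State what location of arrest and place mean, and which years enter the TM comparison.

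The code is a few lines of SAS 9.4. The main work is data: Data collection and variables lists no neighbourhood code, so one must be linked from dispatch records for arrests with no alert, including those of 2013-2014. Intervals will widen somewhat. One of the simulations put this at 0-25% with clustered errors, and at about 30% with neighbourhood fixed effects.
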